One important outcome of this trial will be a prospective assessment of the effect of this alum-adjuvanted vaccine on immune system activation in SLE patients. We plan to assess this using state of the art assays including systemic cytokine measurements, immune cell phenotyping, and single cell sorting of B and T cells to quantify vaccine-induced transcripts. Immune cell activation will be assessed by quantitative polymerase chain reaction (qPCR). We plan to assess changes to the frequency and activation state of both B and T cell populations for this cohort and a group of historical control subjects drawn from a prior study of this vaccine formulation—specifically, RV328, a phase I/II trial assessing the immunogenicity of AIDS VAX® B/E among 40 HIV-uninfected individuals in Thailand. Data obtained for the safety and immune activation outcomes in RV328 will be compared to the AE reports and immunogenicity data obtained in this study, to compare the effects of alum-adjuvanted vaccine administration between healthy subjects and SLE patients. After correction for multiple comparisons, this small study will not be able to detect statistically significant differences between those with SLE and the historical controls. In addition, this study is not powered to identify rare safety events. However, this study will provide a first and critical dataset for participants with SLE to which future HIV-1 vaccine/adjuvant candidates can be compared. In addition, differences observed in this study will provide a dataset to help guide development of future studies and for the assessment of future vaccine candidates in patients with SLE. Given the importance of vaccines in prevention of disease in SLE patients (31, 32, 34, 35, 83), these data will fill a critical gap in current knowledge and inform risk assessments of current and future vaccines. By using the non-replicating component of the only HIV-1 vaccine regimen to have shown any efficacy in preventing HIV-1 transmission, we will obtain information about alum-adjuvanted vaccine immune activation in persons with SLE, and also assess how individuals with SLE can respond to a protein-based HIV-1 vaccine.

### 4.1.3 Potential impact of this study on development of future HIV-1 vaccine candidates

This trial aims to provide information that will inform vaccine design for people who do not have SLE by quantifying the effect that altered immune tolerance has on HIV-1 bnAb development. It has been observed that bnAbs against HIV-1, and specifically antibodies reactive with many different virus subtypes, are not made by the majority of infected patients. When such antibodies are made, they usually occur after several years of infection (84). These bnAbs have a number of characteristics commonly found in autoantibodies, such as long and hydrophobic antigen binding loops, high levels of somatic mutation, and/or polyreactivity with human antigens (85). Antibodies with these characteristics are usually under tolerance control during B cell development and maturation (9, 12, 15), and antibodies reactive with self-antigens are commonly found in patients with defects in immune tolerance (eg, autoimmune diseases such as SLE) (86, 87). Importantly, studies with bnAb knock-in mice have shown that indeed some bnAbs are directly eliminated by numerous tolerance mechanisms including deletion, anergy and receptor editing (9, 15, 17).

In addition, several investigators have noted an underreporting of coincident SLE and HIV-1 infection (10, 29, 88, 89) and early in the HIV-1 epidemic it was speculated that antibody responses in SLE may be protective against HIV-1 infection (11). To date, there have been no prospective studies of either HIV-1 infection or vaccination in patients with autoimmune diseases; thus, whether patients with autoimmune diseases can make qualitatively or quantitatively better responses to HIV-1 vaccine antigens, or to any other type of vaccine, is unknown.

There are, however, data that suggest SLE could be permissive for the development of bnAbs against HIV-1. In mouse studies of bnAb development, B cells expressing these antibodies were subject to strict tolerance control (15, 17). BnAb 2F5 was shown to react with a human antigen; mice that have the same antigenic epitope restrict the creation of 2F5-epitope specific antibodies while opossums that lack the same epitope are not restricted (90). Taken together, these data suggest that some bnAbs are under similar tolerance controls in humans and would be difficult to elicit with vaccines (9, 12, 18). This is corroborated by the fact that none of the large-scale HIV-1 vaccine trials in humans have elicited bnAbs (91). In order to make an effective vaccine against HIV-1, we must determine the roadblocks and potential solutions in order to guide future vaccine development. If patients with SLE are capable of making a better antibody response after HIV-1 vaccination, this will suggest that modulation of tolerance may be required to induce those kinds of responses in people without autoimmune disease.

In support of this idea, a recently published study has shown that the development of bnAbs by individuals with chronic HIV-1 infection is associated with the presence of plasma autoantibodies and with a lower frequency of regulatory CD4+ T cells, a higher frequency of circulating memory T follicular helper (Tfh) CD4+ cells, and a higher T regulatory (Treg) cell level of programmed cell death–

1 expression (92). This vaccine trial in participants with SLE will allow us to assess for these same alterations of T cell populations in this group of vaccine recipients. The data generated by this study will provide critical information as to whether naturally occurring variations in immune tolerance control, as exist in SLE, are permissive for bnAb development.

Thus, a critical question to be posed by this vaccine study is whether the AIDSVAX® B/E immunogen can induce nAbs in patients with known SLE and whether these antibodies can block infection *in vitro*. This is particularly important to test for the AIDSVAX® B/E immunogen, as it was part of the vaccine regimen that induced a modest degree of protection in the RV144 trial (22). Of note, the two participants in RV144 who developed autoimmune disease were studied and did not develop neutralizing breadth in any of the samples tested. Neither were followed beyond the end of the study, and neither were recruited into the follow-on studies, so data collected in this study could provide valuable information about the effects of altered immune tolerance on HIV vaccine immunogenicity. If bnAbs are produced by any SLE patients in this study, we will further evaluate the effect of altered immune tolerance on their production. By measuring potential genetic influences, the specific cytokine milieu, differences in B-cell and T-cell populations, differences in innate immunity, etc., we can attempt to assess for differences that might exist between SLE patients who develop bnAbs and healthy patients who do not. If we are able to determine what is different in those with SLE, we can try simulating these differences in animals to evaluate whether specific interventions with specific effects on immune tolerance induce bnAb development in healthy (non-autoimmune) animals, and—if successful—work towards implementing similar regimens in humans. The results of this study could help guide the development of future vaccine candidates and adjuvant systems that could induce such responses in the general population.

## 4.2 AIDSVAX® B/E

AIDSVAX® B/E is a bivalent HIV gp120 glycoprotein originally developed and manufactured by Genentech Inc. The development and manufacturing rights were subsequently transferred to VaxGen, Inc. and finally transferred to its current developer, GSID. It is a purified mixture of gp120 proteins produced by recombinant DNA procedures using Chinese hamster ovary (CHO) cell expression. The sequences of MN gp120/HIV-1 and A244 gp120/HIV-1 are expressed as fusion proteins where a 27 amino acid sequence found in the glycoprotein D (gD) of herpes simplex virus type 1 is fused to the amino terminus of each protein. MN and A244 rgp120/HIV-1 are combined to produce the bivalent AIDSVAX® B/E vaccine. AIDSVAX® B/E encompasses both subtype B (MN) and subtype E (A244) proteins that are adsorbed onto 600mcg of aluminum as aluminum hydroxide gel suspension as adjuvant.

### 4.3 Trial design rationale

In this study, 16 eligible participants, who have a physician-confirmed diagnosis of SLE as defined by the classification criteria established by the ACR (86, 87) and who are free of HIV-1 infection, will be administered three doses of alum-adjuvanted AIDSVAX® B/E. This will be an open-label single arm study. AIDSVAX® B/E has an extensive safety history in clinical trials (93, 94). Given this, as well as the knowledge that no prior AIDSVAX® B/E vaccinees have developed HIV-1 bnAbs, the inclusion of a concurrent non-SLE control group is not felt to be necessary. We expect that all participants without autoimmune disease in a control arm would have a similar response and not produce bnAbs; we do not expect a concurrent control arm of healthy participants to provide additional information beyond what can be obtained with historical controls. The study group will therefore be compared with an historical control group comprised of non-SLE subjects previously enrolled in RV328, a similar study assessing immunogenicity of AIDSVAX® B/E administered at the same time points as proposed in this study (Day 0 and Months 1 and 6), plus additional later time points not proposed in this study.

With regards to RV328, an analysis of all participants found that 0/40 participants (30 vaccinated with AIDSVAX® B/E, 10 with placebo) developed neutralization breadth. Given the small study size, we will include all 30 AIDSVAX® B/E vaccinees in the historical control group. As previously noted, RV328 was performed in Thailand, and thus cannot be matched for ethnicity or country of origin.

As part of the original Center for HIV-AIDS Vaccine Immunology (CHAVI) program, the CHAVI 005 study examined a group of participants with known autoimmune disease to determine if any had undiagnosed HIV-1 infection, and if their plasma had any evidence of existing neutralizing antibodies that could account for the previously noted disparity between SLE and HIV-1 infection. This cohort, including 100 participants without autoimmune disease and 125 participants with SLE, was recruited from the Duke Lupus Clinic between 2005-2011. The CHAVI program tested this cohort using both HIV-1 antibody and viral load assays and found that none of the participants were HIV-1-infected. Testing of a subset of the participants did not reveal evidence of HIV-1 neutralizing antibodies or reactivity with HIV-1 Env proteins, although it should be noted that the study participants did not receive any HIV-1 vaccinations. Samples from this study are available for testing using the same assays planned for the present study, and for all participants, there are plasma, serum, and PBMC stored in the CHAVI Repository. This cohort was drawn from the same patient population at Duke that will be recruited for this study, and because the second of two sites participating in this study is in Alabama, the demographics of the two populations is likely to be similar. We can therefore use the SLE patients in the CHAVI 005 study as unvaccinated SLE controls, serving as a cross-sectional comparison group.

The primary outcome is to evaluate whether persons with SLE vaccinated with an HIV-1 vaccine will develop HIV-1 nAbs with greater breadth and potency than persons without SLE. In addition, our immunogenicity hypotheses are that this cohort of participants with SLE will make a qualitatively and quantitatively superior antibody response against HIV-1. An additional secondary outcome will address the hypothesis that the vaccine regimen will be safe and well tolerated by participants. The proposed number of participants is not sufficiently powered to detect uncommon or rare events. Participants will be monitored for sentinel events indicative of SLE disease activation (ie, SLE flare); detection of an SLE flare will trigger additional review.

#### **4.3.1 Dose (amount and number)**

The AIDS-VAX® B/E dose of 600 mcg / 1 mL is the same as was used in the RV328, RV144 (22) and VAX003 (33) trials. The sequence of AIDS-VAX® B/E immunizations is similar to that given in all three of these trials, however, we have reduced the number of vaccinations to three (3) to reduce the time needed for completion of the study.

#### **4.3.2 Schedule**

The schedule for AIDS-VAX® B/E was chosen to be consistent with, but shorter than, the schedule used in RV328, RV144 (93) and VAX003 (33). The present study will only use the first 3 immunization timepoints: Day 0 and Months 1 and 6.

Prior vaccine studies using AIDS VAX® B/E did not induce bnAbs either following canarypox priming, as in the RV144 trial (22), or when administered alone, as in the VAX003 trial (33). In these 2 studies, nAbs were restricted to easy-to-neutralize (tier 1) isolates from clade AE circulating recombinant form CRF01\_AE (91). Antigenicity studies of the AIDS VAX® B/E immunogen have shown that Env variable loop 1 and 2 (V1V2) glycan bnAbs such as PG9 and CH01 bind readily to epitopes expressed on the AE.A244 gp120 vaccine components, and the putative naïve B cell receptor of the CH01 bnAb lineage also binds well to the AE.A244 gp120 (97). Thus, the AIDS VAX® B/E immunogen is antigenic for V1V2 bnAbs, but no plasma V1V2 bnAb activity was induced in the RV144 vaccine trial (91). Thus, a secondary hypothesis to be tested in this trial is whether the AIDS VAX® B/E immunogen can induce V1V2 glycan nAbs when administered to trial participants with SLE.

Intriguingly, another vaccine trial (VAX003) administered the same AIDS VAX® B/E immunogen used in the boost phase of RV144 and produced robust Env antibody responses that were higher than those seen in RV144 (33). Despite these responses, VAX003 did not prevent HIV-1 acquisition in a high-risk population of intravenous (IV) drug users in Thailand. It has recently been found that the use of ALVAC and a prime and boost in RV144 induced higher levels of IgG3 Env antibodies than in VAX003 and these IgG3 antibodies against V1V2 correlated with decreased transmission risk (98). Thus, the RV144 vaccine may have been protective because of induction of IgG3 V1V2 responses, but efficacy was limited by minimal potency and short duration of the induced antibody responses (98). These data would suggest that ALVAC priming may be required for V1V2 responses in adults lacking autoimmune disease, thus it will be important to carefully assess for these responses in patients with SLE receiving AIDS VAX® B/E. Furthermore, given concerns over the use of live vector vaccines in patients with SLE (31, 32), determining whether AIDS VAX® B/E alone can elicit V1V2 responses will guide the deployment of future HIV-1 vaccine candidates in this vulnerable population.

#### **4.5 Potential risks of study products and administration**

The vaccine has been extensively tested in healthy populations. Prior work has shown that vaccination of autoimmune disease patients with killed or subunit vaccines are generally well tolerated (99).

**Table 4-1 Summary of potential risks of study products and administration**

Common	
 
• Mild to moderate injection site pain, tenderness, erythema, or swelling/induration/edema
 
• Malaise/fatigue, myalgia, or headache in the first few days following injection
 
• A vaccine-induced positive HIV antibody test result
 

Less common	
 
• Severe injection site pain or tenderness
 
• Fever, chills, flu-like syndrome, arthralgia, rash, nausea, or dizziness in the first few days following injection
 
• Vasovagal reaction/lightheadedness/dizziness related to the injection procedure
 
• Transient changes in clinical laboratory values
 
• Injection site hematoma, bruising/ecchymosis, other transient lesions, itching, or bleeding related to the injection procedure
 

Uncommon or rare	
 
• Severe localized injection site reaction, such as sterile abscess or secondary bacterial infection
 
• Allergic reaction, including rash, urticaria, angioedema, bronchospasm, or anaphylaxis
 
• Muscle damage at the injection site
 

Theoretical risks	
 
• Autoimmune disease or exacerbation of autoimmune disease*
 
• Effects on a participant's response to an approved HIV vaccine administered in the future
 
• Effects on susceptibility to HIV, if the participant is exposed to HIV
 
• Effects on the course of HIV infection/disease, if the participant is infected with HIV
 
• Effects on the fetus and on pregnancy
 

\* See section 4.1.2 for a review of studies evaluating other vaccines in people with SLE and the potential for exacerbation of autoimmune disease. There are no prior studies evaluating AIDVAX B/E® in participants with SLE or other autoimmune disease, and therefore the risk of exacerbating autoimmune diseases is unknown for this study vaccine.

## 5 Objectives and endpoints

### 5.1 Primary objectives and endpoints

*Primary objective 1:*

To evaluate the breadth and potency of HIV-1 nAb responses

*Primary endpoint 1:*

Response rates, magnitude and breadth of nAb responses to the vaccine strains and a global panel of heterologous env-pseudotyped viruses at baseline and two weeks after the third vaccination

*Primary objective 2:*

To examine the safety and tolerability of AIDSVAX® B/E in a population of participants diagnosed with SLE who have stable disease

*Primary endpoints 2:*

- Frequency and severity of local and systemic reactogenicity signs and symptoms
- Laboratory measures of safety: white blood cells (WBC), neutrophils, lymphocytes, hemoglobin, platelets, ALT, complement, anti-dsDNA titers, urinalysis and spot urine protein:creatinine ratio
- Frequency of adverse events categorized by Medical Dictionary for Regulatory Activities (MedDRA) System Organ Class, and MedDRA Preferred Term, severity and assessed relationship to study products; detailed description of all AE meeting DAIDS criteria for expedited reporting
- Measures of SLE disease activity and functional status: Safety of Estrogens in Lupus Erythematosus National Assessment-SLE Disease Activity Index (SELENA-SLEDAI) and Routine Assessment of Patient Index Data (RAPID3)

### 5.2 Secondary objectives and endpoints

*Secondary objective 1:*

To characterize isolated antibodies for evidence of HCDR3-binding CD4 binding site bnAb lineages elicited by the vaccine

*Secondary endpoint 1:*

The degree of somatic hypermutation, length of antibody binding loops and germline gene usage in participants with SLE compared with historical controls after the third vaccination

*Secondary objective 2:*

To assess the induction of bnAb precursors

*Secondary endpoint 2:*

NAb responses to viruses with altered glycosylation, indicative of bnAb precursors, at baseline and two weeks after the second and third vaccinations

*Secondary objective 3:*

To determine the effect of an HIV vaccine on immune system activation

*Secondary endpoint 3:*

Vaccine-induced immune activation as assessed by serum cytokine analysis and B and T cell phenotyping, as well as expression of Treg and Tfh markers one week after the second and third vaccinations

*Secondary objective 4:*

To evaluate the level of HIV-1–specific binding antibody production in response to vaccination

*Secondary endpoint 4:*

Response rate and magnitude of HIV-1–specific IgG binding antibodies at baseline and two weeks after the second and third vaccinations

*Secondary objective 5:*

To further characterize the epitopic specificity of HIV-1 binding antibodies

*Secondary endpoint 5:*

Specificity of antibody responses by epitope mapping of functional and binding antibodies two weeks after the second and third vaccinations

*Secondary objective 6:*

To determine whether CD4+ T-cell responses are associated with the observed antibody responses

*Secondary endpoint 6:*

Response rate, magnitude and polyfunctionality of Env-specific CD4+ T cells 2 weeks after the third vaccination

### **5.3 Exploratory objectives**

*Exploratory objective 1:*

To determine the breadth and potency of the antibody-dependent cellular cytotoxicity (ADCC)-mediating antibody response against HIV-1 to vaccination

*Exploratory objective 2:*

To determine if there are common genetic mutations in this group of SLE participants

*Exploratory objective 3:*

To further evaluate immunogenicity of the vaccine regimen, additional immunogenicity assays may be performed, including on samples from other timepoints

*Exploratory objective 4:*

To conduct analyses related to furthering the understanding of HIV, immunology, vaccines, and clinical trial conduct.

## 6 Statistical considerations

### 6.1 Accrual and sample size calculations

Recruitment for this single arm study will target enrolling 16 low-risk, HIV-uninfected adult participants, aged 18-50, who have also been diagnosed with SLE.

The primary purpose of this study is to explore the possibility that AIDS VAX® B/E may induce bnAbs in a population of participants diagnosed with SLE and to closely monitor participant safety. Since enrollment is concurrent with receiving the first study vaccination, all participants will provide some safety data. However, for immunogenicity analyses, it is possible that data may be missing for various reasons, such as participants terminating from the study early, problems in shipping specimens, low cell viability of processed peripheral blood mononuclear cells (PBMCs). Immunogenicity data from 17 phase 1 and 2 phase 2a HVTN vaccine trials, which began enrolling after June 2005 (data as of September 2014), indicate that 15% is a reasonable estimate for the rate of missing data at day 182. For this reason, the sample size calculations in Section 6.1.2 account for 15% of enrolled participants having missing data for the primary immunogenicity endpoint.

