#### 6.1.2 Sample size calculations for immunogenicity

The primary immunogenicity endpoint will be the production of bnAbs. This will be defined as a nAb geometric mean titer (GMT) greater than 100 against a standard HIV-1 pseudovirus panel. The sample size of 16 was selected such that if the true proportion of participants producing bnAbs in this population is at least 10 percent, we will have 81.5% probability of detecting bnAbs in at least one participant. If there is a dropout rate of 10% then we will still have a 77.1% probability of detecting bnAbs in at least one participant ([Table 6-2](#)).

**Table 6-2 Probability of detecting bnAbs in at least one participant, among different arm sizes, for different true event rates**

Number of Participants	True Population Percentage of SLE Participants Producing BnAbs			
	1%	5%	10%	25%
12	0.114	0.460	0.718	0.968
14	0.131	0.512	0.771	0.982
16	0.149	0.560	0.815	0.990
18	0.165	0.603	0.850	0.994

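### Section 6.1 says the immunogenicity sizing allows for 15% missing data, but Section 6.1.2 shows only a no-loss figure (81.5%) and a 10% dropout figure (77.1%); at 15% the probability is about 76%

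*Combined protocol and SAP*

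**What the plan says.** Section 6.1 sets enrolment at 16 and separates safety from immunogenicity. Every participant contributes some safety data, whereas immunogenicity data may be lost through early termination, shipping problems or poor cell viability. It cites experience from 19 earlier network trials (17 phase 1, 2 phase 2a), whose data "indicate that 15% is a reasonable estimate for the rate of missing data at day 182". It then says that "the sample size calculations in Section 6.1.2 account for 15% of enrolled participants having missing data for the primary immunogenicity endpoint".

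Section 6.1.2 gives the sizing argument, which opens "The sample size of 16 was selected such that if the true proportion of participants producing bnAbs" and takes that proportion to be 10% or higher. On that basis the plan claims that "we will have 81.5% probability of detecting bnAbs in at least one participant". On losses it says only this: "If there is a dropout rate of 10% then we will still have a 77.1% probability of detecting bnAbs in at least one participant". The rows of Table 6-2 are for 12, 14, 16 and 18 participants. The 15% rate appears in neither the text nor the table of Section 6.1.2.

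The 15% rate was estimated at the time point that matters. Primary endpoint 1 in Section 5.1 is assessed "at baseline and two weeks after the third vaccination". Table 3-1 puts the third vaccination on Day 168, and 168 + 14 = 182. Appendix E shows a neutralizing antibody draw at D182.

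**The concern.** The two sections contradict each other. One says a 15% allowance is built in; the other selects the sample size with no loss and then names a different rate.

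Section 6.1.2 is the only sizing statement for the primary immunogenicity endpoint. A reader who accepts Section 6.1 would take 81.5%, or at least 77.1%, as already net of 15% missing data. This bears on how a result of zero producers is read. The printed 81.5% implies an 18.5% chance of seeing none when the true proportion is 10%; under the plan's own missing-data rate that chance is about 24%.

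**Working it through.** **Inputs**

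- Enrolled: n = 16 (Section 6.1).
- True proportion producing bnAbs: p = 0.10 (Section 6.1.2); p = 0.05 is also a column of Table 6-2.
- Missing-data rate: d = 0.15 (Section 6.1); the dropout rate named in Section 6.1.2 is 0.10.

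**Reproducing the plan's figures.** With m evaluable participants, the chance of at least one producer is 1 − (1 − p)^m.

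- m = 16: 1 − 0.9^16 = 0.815, as printed. No loss is included.
- m = 14: 1 − 0.9^14 = 0.771, as printed for 10% dropout.

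The remaining cells of Table 6-2 also reproduce to within 0.001.

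**What loss the 77.1% represents.** A 10% loss leaves 16 × 0.90 = 14.4 evaluable, which the plan takes as 14. Fourteen of 16 is a loss of 2/16 = 12.5%. A 15% loss leaves 16 × 0.85 = 13.6 on average.

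**The missing 15% case, p = 0.10**

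| Treatment of 15% missing | Formula | Probability |
|---|---|---|
| Each participant independently missing | 1 − (1 − 0.10 × 0.85)^16 = 1 − 0.915^16 | 0.759 |
| Average number evaluable, not rounded | 1 − 0.9^13.6 | 0.761 |
| Rounded down to 13 | 1 − 0.9^13 | 0.746 |
| Rounded to nearest, 14 | 1 − 0.9^14 | 0.771 |

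**Gaps, using the independent-missingness value**

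- Against the figure used to choose 16: 81.5 − 75.9 = 5.6 points.
- Against the stated loss scenario: 0.7712 − 0.7586 = 0.0126, or 1.3 points.
- Chance of no producer among those evaluable: 1 − 0.759 = 24.1%, against 1 − 0.815 = 18.5%.

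**At p = 0.05:** 1 − (1 − 0.05 × 0.85)^16 = 0.501, against 1 − 0.95^16 = 0.560 with no loss.

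**How often fewer than 14 are evaluable.** With a binomial(16, 0.85) number evaluable, P(13 or fewer) = 0.439, so P(14 or more) = 0.561.

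**For scale only.** At 15% missing, 1 − 0.915^18 = 0.798 and 1 − 0.915^19 = 0.815, so 19 enrolled would restore 81.5%. With 16 enrolled, 81.5% corresponds to a true proportion of 0.10/0.85 = 11.8%.

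**The case against.** The strongest reply is that 77.1% is already a fair answer at 15%. The expected 13.6 rounds to 14. Under independent missingness, 14 is also the most likely number evaluable (27.8%) and the median. At 10% missing, both the mode and the median are 15, so the 14-participant row suits 15% at least as well as it suits 10%. On this view the fault is a wrong label, not an absent calculation. In addition, the rows for 14 and 12 in Table 6-2 correspond to losses of 12.5% and 25% from 16, so the table brackets the 15% case. A careful reader can also see that 81.5% is a no-loss value, because the table ties it to 16 participants and the dropout sentence follows it. Finally, the study is exploratory and no hypothesis test depends on this probability.

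Much of this stands as to size. Against 77.1% the difference is 1.3 points, and it vanishes if exactly 14 are evaluable. This is a contradiction between two sections, not a computing error, and it does not undermine the design.

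It does not remove the contradiction. The plan labels 77.1% as 10%, no row is tied to 15%, and bracketing a case is not the same as having allowed for it. The figure on which 16 was chosen contains no allowance at all, although Section 6.1 says the calculations include one. Reading dropout as narrower than missing data does not help, because Section 6.1 refers to the full 15%.

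**Conclusion.** The concern holds. Section 6.1 attributes to Section 6.1.2 a 15% missing-data allowance that is not there. At the plan's own rate and a true proportion of 10%, the chance of detecting at least one producer is about 76%, with a range of 74.6% (13 evaluable) to 77.1% (14 evaluable), against the 81.5% used to select 16.

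The 75.9% assumes that participants are missing independently of one another and of whether they produce bnAbs. The conclusion that 15% was not used needs no such assumption; it follows from the text. The correction is worth making because it concerns the stated sizing of a primary endpoint. Its practical effect is small: no analysis, endpoint or decision rule changes.

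**What to change.** In Section 6.1.2, replace the 10% dropout sentence with wording such as:

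> With 15% missing data (on average 13.6 of 16 evaluable), the probability of detecting bnAbs in at least one participant is about 76% if the true proportion is 10% (74.6% with 13 evaluable, 77.1% with 14).

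Label 81.5% as the value with no missing data. Optionally, add a row for 13 participants to Table 6-2: 0.122, 0.487, 0.746 and 0.976 at true proportions of 1%, 5%, 10% and 25%.

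The cost is one sentence and one label, plus the optional row. The stated probability becomes slightly less favourable. Enrolment can stay at 16.
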